2.3. Primary Endpoint

The primary effectiveness endpoint will be duration of effect, defined as the number of days from Treatment Day (Baseline) to the day that GLS severity (Investigator assessment) at maximum frown returns to the Baseline value. The treatment will be considered to remain effective for the amount of time during which GLS severity at maximum frown has not returned to Baseline severity. Duration of effect will be estimated by Kaplan–Meier analysis.

Although the trial is not powered for inferential analysis, this will be the most influential outcome in the overall assessment of the effectiveness of prabotulinumtoxinA 40 Units, compared to prabotulinumtoxinA 20 Units, in treating moderate to severe glabellar lines.

Confidential Page 9/58

TABLE 1. SCHEDULE OF EVENTS AND PROCEDURES

Visit Number	V1 ¹ Screening	V2 ¹	V3	V4 (phone f/u)	V5 to V15 ²	V16 ³ (or Final Visit, or ET)	Unscheduled Visit 11
Day/Week/Month	≤ 14D	Tx Day	48Hr	D 7	D30 to D330 Monthly Visits	D365	
Visit Windows				±1 Day	D30 ±3D, ≥D60 ±7D	±14D	
Assessment and Procedures							
Informed Consent	X						
Inc/Excl Criteria	X						
Demographics, Med Hx	X						
Randomization to Study Tx 4		X					
Effectiveness - Investigator							
Glabellar Line Scale ⁵	X	X	X		X	X	X
Global Aesthetic Improvement			X		X	X	X
Effectiveness - Subject							
Glabellar Line Scale ⁵	X	X	X		X	X	X
7-Day Subject Diary		Х —		—			
Global Aesthetic Improvement			X		X	X	X
Subject Satisfaction Score			X		X	X	X
Clinical Interview 6					D30 only	X	X
Safety Evaluations							
Directed Questionnaire ⁷	X		X		X	X	X
Directed Review of Systems	X		X		X	X	X
Vital Signs 8	X		X		X	X	X
Physical Exam 9	X		X		X	X	X
UPT (as applicable)	X	X				X	
Clinical Laboratory Tests 10	X					X	X
ECG	X					X	X
Safety Assessment Phone Call				X			
Brow Area Photography	X	X	X		X	X	X
Concomitant Medications	X	X	X	X	X	X	X
AE Assessment		X	X	X	X	X	X

- 1. Screening and treatment visit can take place the same day, at the discretion of the investigator
- 2. Subjects will be followed monthly until their Glabellar Line Scale score is back to Baseline (Investigator assessment)
- 3. Subject exits study once their Glabellar Line Scale Score has returned to Baseline (Investigator assessment)
- 4. IP may be administered same day as Screening
- 5. Glabellar Line Scale at Maximum Frown, 0=none, 1=mild, 2=moderate, 3=severe
- 6. Clinical Interview Questions
 - What did you like about the treatment (clinically or other feedback)?

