7. STATISTICAL METHODS

7.1. Primary Effectiveness Endpoint

The primary effectiveness endpoint will be duration of effect (regardless of responder status), defined as the number of days from Treatment Day (Baseline) to the day that GLS severity (Investigator assessment) at maximum frown returns to the Baseline value. Although the trial is not powered for inferential analysis, this will be the most influential outcome in the overall assessment of the effectiveness of prabotulinumtoxinA 40 Units, compared to prabotulinumtoxinA 20 Units, in treating moderate to severe glabellar lines. Analysis will be performed using the modified Intent-To-Treat (mITT) population and regardless of responder status.

Duration of effect will be described by Kaplan-Meier curves and the respective median times with associated 2-sided 95% confidence interval (CI) for each treatment group. Statistical analyses of treatment group differences will be done using Cox proportional hazards regression with time to return to Baseline as the dependent variable, treatment group as the independent variable, and age, gender, and Baseline GLS score (Investigator assessment) at maximum frown as covariates.

Statistical significance will be established at the 0.025 level with one-sided hypothesis testing.

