7.6. Sample Size Considerations

This study is not powered for inferential analyses. Approximately 150 subjects will be randomized to the study, 50 subjects in each of the three treatment arms; 20U onabotulinumtoxinA, 20U prabotulinumtoxinA and 40U prabotulinumtoxinA. Assuming 50 subjects per treatment group, exponential distributions for failure and censoring times, a median duration of effect of 4 months in the reference group, and an annual censoring rate of 10%, the study will have 80% power to detect a hazard ratio of 0.47 based on a one-sided hypothesis test of the primary effectiveness endpoint with alpha = 0.025. As such, it is the opinion of the study Sponsor that 50 subjects per group (total sample size n=150) will be sufficient to address the objectives of this study.

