7.7. General Considerations

Data will be listed by subject number. Data will be summarized by treatment and study visit, where applicable. For categorical parameters, the number and percentage of subjects/observations in each category will be presented; percentages will be based on the number of subjects in the relevant analysis population in each treatment group. For continuous parameters, descriptive statistics will include n (number of subjects or observations), mean, standard deviation, median, and range. A full description of the statistical methods planned for this study will be provided in the Statistical Analysis Plan (SAP). All programs for data output and analyses will be written in SAS version 9.4 or higher (SAS Institute, Inc., Cary, NC).

Missing Values: For the mITT analysis of primary, secondary, tertiary, and exploratory duration of effectiveness endpoints, in the case of a missed visit, subjects will be considered to have returned to Baseline if they are confirmed to have returned to Baseline at the next non-missed visit. Subjects will be considered to have to have returned to Baseline if they fail to attend 2 consecutive visits or drop out of the study. For missing observations for exploratory endpoints other than duration of effect data will be analyzed as observed without imputation.

Discontinuation and Drop-Outs: Dropouts will not be replaced. Subject disposition will summarize the number of subjects who were randomized and who discontinued from the study (including reasons for discontinuation).

Interim Analysis: An interim analysis will be conducted when >90% of subjects have completed Visit 8 (Day 120) to evaluate response to exposure (efficacy, duration) and adverse events. For assessment of the primary effectiveness endpoint, 95% CIs will be presented but statistical analyses will not be conducted and a statistical penalty for the final analysis will not be employed. While data by treatment group will be presented, individual subjects will not be unblinded.

Poolability of Investigative Sites: Data from all investigative sites will be pooled based on the assumption of clinical comparability: the same protocol will be used for all sites, all sites will be monitored for protocol compliance, and the same data collection instrument and methodology will be used across all sites.

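### Return to Baseline is interval-censored between visits about 30 days apart, but SAP 7.1 plans only right-censored Kaplan-Meier and Cox, so absolute medians can be off by about two weeks

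*SAP*

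**What the plan says.** - SAP 7.1 defines the primary endpoint as the number of days from treatment until the Investigator's GLS at maximum frown is back at its Baseline value. The footnote to SAP Table 14.3.1.1 also counts the duration in days from Visit 2.
- For description, 7.1 states: "Duration of effect will be described by Kaplan-Meier curves and the respective median times". For comparison it specifies "Cox proportional hazards regression with time to return to Baseline as the dependent variable", and adds: "Statistical significance will be established at the 0.025 level with one-sided hypothesis testing".
- SAP Table 1 (Schedule of Events, section 2.3) puts the post-treatment Investigator GLS at 48 hours, then "D30 to D330 Monthly Visits", then Day 365. The Day 7 contact is a phone call without GLS. Windows are ±3 days at Day 30, ±7 days from Day 60 and ±14 days at Day 365. Unscheduled visits may include a GLS.
- For a gap in attendance, SAP 7.7 (Missing Values) has this rule: "subjects will be considered to have returned to Baseline if they are confirmed to have returned to Baseline at the next non-missed visit". It also counts dropout, or two consecutive missed visits, as return to Baseline.
- Neither document gives an interval-censored method, a midpoint rule, an explicit event-dating rule or a method for ties.

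**The concern.** The day of return is never observed. For an attended visit, the only facts are that the subject had not returned at the previous assessment and had returned at this one. Kaplan-Meier and Cox need a single date, and the only one on record is the visit that detects the return. The SAP does not say that this date is used; it follows from the data collected. Dated this way, the event is always placed at the late end of its interval. After a missed visit there are two candidate dates about 30 days apart, and 7.7 does not say which applies.

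Median duration in days is the main descriptive figure of a trial about duration, and the same methods carry over to the secondary and exploratory duration endpoints (SAP 7.2 and 7.3). There is a second, conditional risk: if many subjects share the same event day, the choice of tie method affects the Cox hazard ratio and power.

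**Working it through.** **Inputs.** From SAP 7.6: 50 subjects per arm, exponential times, "a median duration of effect of 4 months in the reference group" (about 122 days), "an annual censoring rate of 10" percent, hazard ratio 0.47, one-sided alpha 0.025. From SAP Table 1: visit days and windows. Assumptions not in the documents: Weibull shapes 2.5 and 4 as a range beside the SAP's exponential (shape 1), and visits either exactly on nominal days or uniform within the windows.

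**1. The plan's own figure.** SAP 7.6 states that "the study will have 80% power to detect a hazard ratio of 0.47 based on a one-sided hypothesis test". Expected events per arm = n·λ/(λ+c)·(1−exp(−(λ+c)·12)), with λ₀ = ln2/4, λ₁ = 0.47·λ₀ and c = −ln(0.9)/12 per month. This gives 42.2 + 29.9 = 72.1 events. Schoenfeld power = Φ(½·√72.1·|ln 0.47| − 1.96) = Φ(1.245) = 89.3%. The stated 80% is not reproduced with 12 months of follow-up; 7 months would give 80.2%. Section 7.6 does not state the follow-up used, the gap is conservative, and it does not bear on this point.

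**2. Size of the delay.** If a return falls anywhere in a 30-day interval with equal chance, the next visit comes 30/2 = 15 days later on average. On a median of 122 days that is 15/122 = 12%.

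**3. True 40U medians.** 122·0.47^(−1/shape) gives 259, 165 and 147 days for shapes 1, 2.5 and 4.

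**4. Simulation, dropouts censored** (50 v 50, 1,000 runs per row). Medians are averages over runs in days, exact event date → detecting-visit date.

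| Shape | Visits | Control median | 40U median | HR exact / Breslow / Efron | Power exact / Breslow / Efron | Distinct times |
|---|---|---|---|---|---|---|
| 1 | nominal | 122.7 → 138.0 | 256.8 → 271.4 | 0.468 / 0.489 / 0.468 | 0.888 / 0.862 / 0.886 | 12.4 |
| 1 | windows | 122.3 → 138.2 | 256.6 → 273.5 | 0.467 / 0.470 / 0.468 | 0.898 / 0.894 / 0.894 | 55.4 |
| 2.5 | nominal | 121.9 → 137.2 | 164.4 → 179.7 | 0.466 / 0.532 / 0.475 | 0.945 / 0.883 / 0.943 | 10.8 |
| 2.5 | windows | 121.7 → 137.3 | 164.7 → 180.2 | 0.469 / 0.479 / 0.475 | 0.934 / 0.923 / 0.927 | 65.9 |
| 4 | nominal | 121.5 → 137.9 | 146.7 → 160.3 | 0.466 / 0.580 / 0.491 | 0.947 / 0.789 / 0.926 | 7.3 |
| 4 | windows | 121.6 → 137.6 | 146.7 → 161.4 | 0.460 / 0.489 / 0.481 | 0.948 / 0.918 / 0.924 | 54.8 |

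The shifts run from 13.6 to 16.9 days. The difference between arms moves by about 1 day or less, except at shape 4 on nominal days, where it goes from 25.2 to 22.4.

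**5. The same with the 7.7 dropout rule** (windows, 1,500 runs; the ranges cover dating a dropout at the last attended or the first missed visit).

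| Shape | Control (true 122) | 40U |
|---|---|---|
| 1 | 128.7–130.2 | 242.0–245.0 (true 259) |
| 2.5 | 132.9–133.6 | 173.1–174.0 (true 165) |

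Under exponential times the difference between arms narrows from 134.0 to 113.3–114.8 days. Step 4 does not show this, so it comes from the dropout rule and not from visit dating.

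**6. Interval-censored fit** (Weibull, dropouts censored, visits within windows, 400 runs). Exponential: HR 0.473, medians 121.5 and 253. Shape 2.5: HR 0.470, medians 121.4 and 164.2. The bias largely disappears, with the exponential 40U median 6 days short of 259. The HR is close to that from Cox with Efron ties.

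**The case against.** The strongest reply is that the primary question is 40U against 20U. All arms share one visit schedule, so the delay is nearly the same in both and largely drops out of the contrast. Both documents say that the trial is not powered for inferential analysis. The simulated one-sided rejection rate at a true hazard ratio of 1 was 1.6 to 2.4%, so no false-positive inflation was seen. The log-rank p-values in the SAP table shells do not depend on a Cox tie approximation. All of this stands, and it confines the main harm to the absolute durations.

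A reader might infer two stronger things:

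- **Every reported median is too long.** The documents do not support this. The 7.7 rule that counts dropout as return shortens durations, and under the SAP's own exponential and 10% per year assumptions it makes the 40U median too short (step 5).
- **The hazard ratio is bound to be pulled toward 1 by heavy ties.** This is not established either. Time is counted in days, the windows spread the visits, and the SAP names SAS 9.4 or higher but no tie method. With visits spread over the windows there are about 55 to 66 distinct times, and Breslow costs 3 power points or less.

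Turnbull also has a limit. On nominal visit days it locates the median only to an interval, for example 109 to 139 days for a true 122. Spread over the windows it recovers about 122.

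**Conclusion.** The concern holds for absolute durations. Return to Baseline is interval-censored and the plan has no method for that. Dating it at the detecting visit lengthens each arm's median by about 14 to 17 days on average with dropouts censored, for a 4-month control median. Under the SAP's dropout rule the net error is smaller in the control arm (about 7 to 12 days long). In the 40U arm it ranges from about 14 to 17 days short (exponential) to about 8 to 9 days long (shape 2.5). Two opposing errors that depend on the unknown time distribution and dropout rate cannot be relied on to cancel.

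For the hazard ratio the concern is conditional. With Breslow ties and visits on nominal days, 0.47 becomes 0.49 under exponential times, costing about 3 power points, and attenuation is larger at the assumed shapes 2.5 and 4. With Efron ties or spread-out visits the effect is small. With dropouts censored, the difference between medians hardly changes.

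These sizes rest on the SAP 7.6 planning values, the assumed Weibull shapes and the assumed timing within windows. The absence of a method, a dating rule and a tie rule rests on the documents alone.

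**What to change.** - **SAP 7.1, description:** report medians and confidence intervals from an interval-censored estimator, using the interval (last visit not at Baseline, first visit at Baseline], beside the visit-date Kaplan-Meier. Use Turnbull, or a parametric or midpoint version if visits fall on nominal days.
- **SAP 7.1, comparison:** state that actual assessment dates are used and name Efron or exact ties. Add an interval-censored proportional hazards model as a sensitivity analysis.
- **SAP 7.7:** state which date applies when a return is confirmed after a missed visit.

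No new data or visits are needed. The cost is SAP wording and a little more analysis, and reported absolute durations may be up to about two weeks shorter.

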7.2. Secondary Effectiveness Endpoints

Secondary effectiveness endpoints will be used to provide additional analyses regarding duration of effect of prabotulinumtoxinA 40U, prabotulinumtoxinA 20U, and onabotulinumtoxinA 20U. As duration of effect outcomes, secondary effectiveness endpoints will be assessed as described above for the primary endpoint. The mITT population will be used for summaries and comparisons. Secondary endpoints, in order of importance, will be:

- 1. Duration of effect (PraB vs. OnaB only, regardless of responder status), defined as the number of days from Treatment Day (Baseline) to the day that GLS severity (Investigator assessment) at maximum frown returns to the Baseline value.
- 2. Duration of effect (all treatment groups, regardless of responder status), defined as the number of days from Treatment Day (Baseline) to the day that GLS severity (subject assessment) at maximum frown returns to the Baseline value.
- 3. Duration of effect (all treatment groups) in GAIS responders (score of 2 or 1 at Day 30) as assessed by Investigator.
- 4. Duration of effect (all treatment groups) in GAIS responders (score of 2 or 1 at Day 30) as assessed by subject.
- 5. Duration of effect (all treatment groups) in SSS responders (score of 2 or 1 at Day 30) as assessed by subjects.

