#### 5.1 Inclusion Criteria

A subject must meet the following key criteria in order to be eligible for enrollment in the study:

- 1. Outpatient, male or female of any race, 18 years of age or older.
- 2. Female subjects of childbearing potential must have a negative UPT during Visit 1 (Screening), Visit 2 (if applicable) and practice a reliable method of contraception for the duration of the study.

A female is considered of childbearing potential unless she is:

- postmenopausal for  $\geq 12$  months prior to study treatment administration;
- without a uterus and/or both ovaries; or
- has been surgically sterile for  $\geq 6$  months prior to study treatment administration.

Reliable methods of contraception are:

- hormonal methods (contraceptive pill or implant) or IUD in use  $\geq 90$  days prior to enrolment;
- barrier methods (e.g., diaphragm w/ spermicide or condom w/ spermicide in use  $\geq 14$  days prior to study treatment administration; or
- partner vasectomized  $\geq 3$  months (or confirmed '0' sperm count) prior to enrolment.

[Exception: Females of childbearing potential who are not sexually active are not required to practice a reliable method of contraception. These subjects may be enrolled at Investigator's discretion if they are counseled to remain sexually inactive during the study or agree to use an approved method of contraception should they become sexually active and understand the possible risks in getting pregnant during the study.]

- 3. Moderate to severe glabellar lines (i.e., score of 2 or 3) on maximum frown as assessed by the investigator using the GLS.
- 4. Subject has moderate to severe glabellar lines (i.e., score of 2 or 3) at maximum frown as assessed by the subject using the GLS.
- 5. Able to follow study instructions and likely to complete all required visits.
- 6. Sign the IRB-approved ICF prior to any study-related procedures being performed.

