#### 12.2 Secondary Endpoints

Secondary effectiveness endpoints will be used to provide additional evidence of prabotulinumtoxinA 40 Units superiority to prabotulinumtoxinA 20 Units. As duration of effect outcomes, secondary effectiveness endpoints will be assessed as described above for the primary endpoint. The mITT population will be used for summaries and comparisons. Secondary endpoints, in order of importance, will be:

- 1. Duration of effect, defined as the number of days from Treatment Day (Baseline) to the day that GLS severity (subject assessment) at maximum frown returns to the Baseline value.
- 2. Duration of effect in GAIS responders (score of 2 or 1) as assessed by Investigator.
- 3. Duration of effect in GAIS responders (score of 2 or 1) as assessed by subject.
- 4. Duration of effect in SSS responders (score of 2 or 1) as assessed by subjects.

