14.3.2 Secondary Effectiveness Endpoints – Duration of Effect

Table 14.3.2.1 Duration of Effect (Investigator; Regardless of Responder Status; PraB vs OnaB)

GLS (Investigator) Duration of Effect	PraB 40	OnaB 20	PraB 20	OnaB 20
(Return to Baseline GLS score)	$(\mathbf{n} = \mathbf{x}\mathbf{x})$	$(\mathbf{n} = \mathbf{x}\mathbf{x})$	$(\mathbf{n} = \mathbf{x}\mathbf{x})$	$(\mathbf{n} = \mathbf{x}\mathbf{x})$
Subject Status, n (%)				
Returned to BL (event)	xx (xx%)	xx (xx%)	xx (xx%)	xx (xx%)
Censored	xx (xx%)	xx (xx%)	xx (xx%)	xx (xx%)
Kaplan-Meier Estimates for Return to B	L			
1 st Quartile, (95% CI)	x.x(x.x, x.x)	x.x(x.x, x.x)	x.x(x.x, x.x)	x.x(x.x, x.x)
Median, (95% CI)	x.x(x.x, x.x)	x.x(x.x, x.x)	x.x(x.x, x.x)	x.x(x.x, x.x)
3 rd Quartile, (95% CI)	x.x(x.x, x.x)	x.x(x.x, x.x)	x.x(x.x, x.x)	x.x(x.x, x.x)
Adjusted Hazard Ratio (95% CI)	x.xx (x.xx,	, x.xx)	x.xx (x.xx, x.xx)	
Stratified Log-Rank p-value	p <x.xx< td="">xx	p<x.xxxx< td=""></x.xxxx<>	</x.xx<>	xx	p <x.xxxx< td=""></x.xxxx<>	
Unadjusted Hazard Ratio (95% CI)	x.xx (x.xx,	, x.xx)	x.xx (x.xx, x.xx)	
Unstratified Log-Rank p-value	p <x.xx< td="">xx	p<x.xxxx< td=""></x.xxxx<>	</x.xx<>	xx	p <x.xxxx< td=""></x.xxxx<>	

Data for all subjects regardless of Responder status

Duration of effect in days, calculated from Visit 2 (Treatment Day) to when subject returns to Baseline GLS score Responder = At least 1-Point improvement in GLS (max frown)

Version 1.1 31-May-2023 Confidential Page 30/58

Table 14.3.2.2 Duration of Effect (Subject; Regardless of Responder Status)

GLS (Subject) Duration of Effect (Return to Baseline GLS score)	PraB 40 (n = xx)	PraB 20 (n = xx)	PraB 40 (n = xx)	OnaB 20 (n = xx)	PraB 20 (n = xx)	OnaB 20 (n = xx)
Subject Status, n (%)						
Returned to BL (event)	xx (xx%)	xx (xx%)	xx (xx%)	xx (xx%)	xx (xx%)	xx (xx%)
Censored	xx (xx%)	xx (xx%)	xx (xx%)	xx (xx%)	xx (xx%)	xx (xx%)
Kaplan-Meier Estimates for Return to B	BL					
1 st Quartile, (95% CI)	x.x(x.x, x.x)	x.x(x.x, x.x)	x.x(x.x, x.x)	x.x(x.x, x.x)	x.x(x.x, x.x)	x.x(x.x, x.x)
Median, (95% CI)	x.x(x.x, x.x)	x.x(x.x, x.x)	x.x(x.x, x.x)	x.x(x.x, x.x)	x.x(x.x, x.x)	x.x(x.x, x.x)
3 rd Quartile, (95% CI)	x.x(x.x, x.x)	x.x(x.x, x.x)	x.x(x.x, x.x)	x.x(x.x, x.x)	x.x(x.x, x.x)	x.x(x.x, x.x)
Adjusted Hazard Ratio (95% CI)	x.xx (x.xx,	, x.xx)	x.xx (x.xx	, x.xx)	x.xx (x.xx,	x.xx)

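### Subject-rated GLS durations are adjusted for the Investigator's Baseline grade but not for the subject's own grade, which sets the event; adding it is a small, nearly free gain

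*SAP*

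**What the plan says.** SAP 7.2 item 2 defines the event as the day on which "GLS severity (subject assessment) at maximum frown returns to the Baseline value". The shell for Table 14.3.2.2 labels the outcome "GLS (Subject) Duration of Effect (Return to Baseline GLS score" and brings in no Investigator score.

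For the analysis, SAP 7.2 states that "secondary effectiveness endpoints will be assessed as described above for the primary endpoint". The method it points to, in SAP 7.1, is a Cox regression on treatment with "age, gender, and Baseline GLS score (Investigator assessment) at maximum frown as covariates". Protocol 12.1 and 12.2 have the same model and the same cross-reference. SAP 7.3 refers its duration endpoints, including the subject-rated ones, back to the survival methods already described. Nowhere is the rater of the Baseline covariate changed, and the shells show an adjusted hazard ratio without listing covariates.

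The two Baseline grades are separate measurements. Protocol 5.1 requires, for one criterion, "Moderate to severe glabellar lines (i.e., score of 2 or 3) on maximum frown as assessed by" the investigator and, for another, "Subject has moderate to severe glabellar lines (i.e., score of 2 or 3) at maximum frown as assessed by the subject using the GLS". No agreement between them is required. Protocol 10.2.2 has both raters score before injection at Visit 2.

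**The concern.** A subject who self-rates 2 at Baseline has the event on returning to 2; one who self-rates 3 has it on returning to 3. How far the rating must climb depends on the subject's own grade. The model conditions on the other rater's grade, which agrees with it only in part.

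Leaving a prognostic covariate out of a Cox model pulls the treatment hazard ratio toward 1 and loses some precision. Chance imbalance between arms in the subject's grade would also go unadjusted in the reported hazard ratio. Since the SAP exists to fix methods before database lock, a programmer following it literally would fit the Investigator's grade alone, and a later switch would be an unplanned change.

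**Working it through.** **1. Which tables are affected.** The mechanism needs an event set by the subject's Baseline grade, and both grades present in the analysis set.

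| Table | Event | Subject Baseline grades possible | Applies? |
|---|---|---|---|
| 14.3.2.2 (all subjects) | return to Baseline | 2 and 3 | yes |
| 14.3.3.2.1 (1-point) | return to Baseline | 2 and 3 | yes |
| 14.3.3.2.2 (2-point) | return to Baseline | 2 (to 0) and 3 (to 1 or 0) | yes |
| 14.3.3.2.3 (3-point) | return to Baseline | 3 only (3 to 0 on a 0–3 scale) | no, covariate constant |
| 14.3.3.2.4 (score 0 or 1) | return to Baseline | 2 and 3 | yes |
| 14.3.3.2.5 (1-point at Day 30) | return to Baseline | 2 and 3 | yes |
| 14.3.3.2.6 (loss of response) | score 2 or higher | 2 and 3 | no, same threshold for all |

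**2. The plan's own power figure.** There is none for this endpoint. For the primary endpoint, SAP 7.6 gives 80% power at hazard ratio 0.47, 50 per arm, reference median 4 months, 10% annual censoring, one-sided 0.025. Expected events per arm are 50 × λ/(λ+η) × (1 − exp(−(λ+η) × 12)), with η = −ln(0.9)/12 = 0.0088 per month.
- Reference arm: λ = ln 2/4 = 0.1733, giving 42.2 events.
- 40U arm: λ = 0.47 × 0.1733 = 0.0814, giving 29.8 events.
- Total 72.1 before rounding. Schoenfeld: √(72.1/4) × |ln 0.47| − 1.96 = 1.25, or 89.3% power. Freedman gives 86.5% and a Wald test on the log hazard ratio 88.4%.

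So the stated 80% is not reproduced from these inputs with 12 months of follow-up for all; it is conservative. That is a separate matter and does not affect this point.

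**3. Effect of the mismatch, ignoring the exit rule.** The documents give neither rater agreement nor the prognostic effect of Baseline grade, so both are varied. Cox simulation, 2,000 runs per scenario, 50 per arm, hazard ratio 0.47, 12 months, 10% annual censoring, half self-rating severe. Power with the subject's grade versus the Investigator's grade:

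| Agreement | Grade HR 1.5 | Grade HR 2 | Grade HR 3 |
|---|---|---|---|
| 100% | no difference | no difference | no difference |
| 90% | 88.0 vs 87.6% | 88.2 vs 86.6% | 88.0 vs 84.3% |
| 80% | 88.7 vs 88.1% | 87.4 vs 84.3% | 87.5 vs 80.9% |
| 70% | 88.6 vs 87.2% | 88.0 vs 84.6% | 89.1 vs 77.7% |
| 50% | 88.4 vs 87.2% | 88.4 vs 84.2% | 87.2 vs 75.4% |

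The loss runs from 0 to 87.2 − 75.4 = 11.8 points. The estimated hazard ratio moves from about 0.465 to at most about 0.52.

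At a true hazard ratio of 0.55, 60% self-rating severe and 65% agreement (600 runs), power with the Investigator's grade, the subject's grade, or both is 75/76/77%, 70/74/74% and 60/74/73% for grade hazard ratios 1.5, 2 and 3. Carrying both grades therefore costs nothing visible against the subject's grade alone.

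**4. With the exit rule.** These figures are too large for the planned analysis. Subjects leave when the Investigator's rating returns to Baseline (SAP 2.1; Protocol 10.2.5, from Day 90), so subject-rated follow-up is cut short. Monthly visits and this exit from month 3 were added, with a rater-time correlation of 0.6 and exit before the subject's own event treated as censoring. Both are assumptions. The share of subjects with an observed event falls from about 72–77% to 52–54%. Gain from carrying both grades rather than the Investigator's alone:
- One set of runs (500 per scenario): about 0, 1 and 3 points at 80% agreement, and about 1, 2 and 8 at 65%, for grade hazard ratios 1.5, 2 and 3. The standard error of a single power figure is at most √(0.25/500) = 2.2 points.
- A second set over the same ranges: about 1 to 5 points, with the hazard ratio about 0.01 to 0.03 further from 1.

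**5. Under no treatment effect** (agreement 70%, grade hazard ratio 3, no exit rule): one-sided type I error is 0.021 with the Investigator's grade and 0.023 with the subject's.

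**The case against.** The plan's covariates match its stratification factors (Baseline GLS, age group, gender), and one prespecified set across endpoints is defensible. Treatment is randomized, so an omitted covariate does not invalidate the test. The trial is described as not powered for inference. The shell for Table 14.3.2.2 reports log-rank p-values and no Cox p-value, so a further Cox covariate would change only the adjusted hazard ratio and its interval. Every driver of the simulated loss is assumed.

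All of this stands, and it limits the point to precision and mild attenuation. It does not explain why the grade that defines the event is left out when it is already collected.

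Three stronger readings are tempting and not supported:
- A reader might infer that the Investigator's grade is simply the wrong covariate and should be replaced. The Investigator's return to Baseline triggers exit, so that grade bears on how long subject ratings are observed and belongs in the model.
- A reader might infer that every subject-rated GLS table needs the change. Tables 14.3.3.2.3 and 14.3.3.2.6 do not, for the reasons in the first table of the working.
- A reader might infer that randomization leaves the subject's grade unbalanced. Protocol 6.2 and SAP 3.2 stratify on Baseline GLS without naming the rater, so this cannot be established.

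**Conclusion.** The mismatch is real on the text of both documents and its consequence is small. With Investigator-triggered exit, 65–80% agreement and a grade hazard ratio of 1.5 to 3, the expected gain is about 1 to 5 power points. One set of runs reached 8, at 65% agreement and a grade hazard ratio of 3. If the raters nearly always agree, or Baseline grade is hardly prognostic, the gain is nil.

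A reader might take the 12- to 14-point differences seen without the exit rule as the cost to this trial. They are not, because they assume follow-up to 12 months whatever the Investigator scores. Nor is there a false-positive risk, and the primary endpoint, where event and covariate share a rater, is unaffected. Severity is minor: an improvement worth making because it is nearly free.

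**What to change.** In SAP 7.2 item 2 and SAP 7.3 item 1, state that for Tables 14.3.2.2, 14.3.3.2.1, 14.3.3.2.2, 14.3.3.2.4 and 14.3.3.2.5 the adjusted hazard ratio comes from a Cox model with treatment, age, gender, Investigator Baseline GLS and the subject's own pre-injection Visit 2 GLS. Leave Tables 14.3.3.2.3 and 14.3.3.2.6 and all Investigator-rated analyses as they are. In the same edit, name the rater of the Baseline GLS stratum in SAP 3.2.

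The cost is a sentence or two in the SAP and one degree of freedom in the affected models; no new data are needed.
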